years) vs. adult ≥ 18 years), chronicity of Norovirus-associated symptoms (acute (<14 days) vs. chronic (≥ 14 days)) and transplant type (solid organ (SOT) vs. hematopoietic stem cell transplant (HSCT)). Enrolled subjects will participate in 2 phases of the study: Treatment Phase, which will include dosing with the assigned study agent for 28 days and study visits on study Day 1, 7 ± 3 days, 14 ± 3 days, 21 ± 3 days, and 28 ± 3 days; Longitudinal Monitoring Phase which will include telephone call on Days 35 ± 3 days, 53 ± 7 days, 113 ± 7 days, 173 ± 7 days. study visits on study Day 60 ± 14 days, 120 ± 14 days and 180 ± 14 days. If symptoms recur after completion of the Treatment Phase, subjects can resume any therapy excluding nitazoxanide at the discretion of the principal investigator or his/her designee. Nitazoxanide can be used after Day 28 if the local PI attests that it is medically urgent to use the nitazoxanide because the patient is experiencing severe or life-threatening disease. Although nitazoxanide can be used if it is felt critical to the subjects care, its use should be avoided until Day 180 whenever felt to be safe to do so by the local PI. Additional stool specimens should be collected prior to initiation of therapy for testing in the central lab.

Estimated Time to Complete Enrollment: 60 months.

Schematic of Study Design:

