	500mg	\geq 18	10.6 (2.0)	3.0 (2-4)	41.9 (6.0)	10.5 (1.4)	4.5 (4-6)	63.0 (12.3)

¹Mean (\pm SD). ²Mean (Range)

Administration of the tablet with food increased the AUC_t of tizoxanide and tizoxanide glucuronide in plasma almost two-fold and the C_{max} by almost 50%. Likewise, administration of the suspension with food increases the AUC_t of tizoxanide and tizoxanide glucuronide by about 45-50% and the C_{max} by ≤10%. It is recommended to always take nitazoxanide with food to ensure maximal delivery of the active drug. Repeat dosing of nitazoxanide every 12 hours for 7 consecutive days failed to demonstrate

significant accumulation of nitazoxanide metabolites tizoxanide or tizoxanide glucuronide detected in plasma.

In plasma, the parent drug, nitazoxanide is generally not detected while 99% of tizoxanide is bound to proteins. Following oral administration in humans, nitazoxanide is rapidly hydrolyzed to an active metabolite, tizoxanide (desacetyl-nitazoxanide). Tizoxanide then undergoes conjugation, primarily by glucuronidation. *In vitro* metabolism studies have demonstrated that tizoxanide has no significant inhibitory effect on cytochrome P450 enzymes. (Alinia® (nitazoxanide) Prescribing Information. Romark, L.C., Tampa, FL. November 2013)

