7 STUDY SCHEDULE

The study will need to enroll 160 subjects who meet inclusion and exclusion criteria and agree to participate in the study (*Section 5.1, 5.2-Subject Inclusion Criteria, Subject Exclusion Criteria*).

Upon enrollment in the study, subjects will be randomized into two treatment groups: active nitazoxanide and placebo:

- a. Nitazoxanide Arm: All subjects age ≥ 12 years: 500 mg (one tablet) nitazoxanide by mouth twice daily with food for 56 consecutive doses.
- b. Placebo Arm: All subjects age ≥ 12 years: Placebo (one tablet) by mouth twice daily with food for 56 consecutive doses.

Randomization will be stratified by age group (adult vs. pediatric), chronicity of Norovirus-associated symptoms (acute vs. chronic) and transplant type (HSCT vs. SOT) as follows:

- Duration of Symptoms: onset of Norovirus-associated symptoms (diarrhea, nausea and/or abnormal appetite) < 14 days vs. ≥ 14 days
- Transplant Type: solid organ vs. hematopoietic stem cell transplant
- Age Range: pediatric (12-17 years) vs. adult ≥ 18 years

Both investigators and subjects will be blinded to study treatments. Subjects will take study product preferably with food for 56 consecutive doses. If the study subject has an episode of emesis or spits out the study medication within one hour of administration, the event will be documented in the subject's record and then the full dose will be re-administered one time only per scheduled dose. All subjects must have therapy discontinued after taking 56 doses.

If a subject misses a dose, they will be instructed to skip that dose and resume taking their next dose as scheduled and to record the missed dose on their Subject Diary.

If symptoms recur after discontinuing therapy, subjects can resume any therapy at the discretion of the principal investigator or his/her designee with the exception of nitazoxanide.

Nitazoxanide can be used after Day 28 if the local PI attests that it is medically urgent to use the nitazoxanide because the patient is experiencing severe or life-threatening disease. Although nitazoxanide can be used if it is felt critical to the subjects care, its use should be avoided until Day 180 whenever felt to be safe to do so by the local PI. Any use of nitazoxanide beyond Day 28 will be documented on the concomitant medication form and prescribed from commercial

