Subjects will be given a paper diary (to inquire about symptoms and severity along with overall well-being) that will be completed daily, at the time of study product dosing. The time of study product dosing will also be recorded. This will be completed on a daily basis through day 28. The pack of paper diary along with instructions that is given at enrollment will cover the entire study period.

The stool sample must have been produced within 24 hours of the visit and if it exceeds 24 hours it must be disposed. Subject would be encouraged to provide another sample within the visit window and if not, a rectal swab may be used for virus detection.

b. Study Day 7 ± 3 days

- Collection and review of completed diary pages.
- WBC, TLC, Hb, Platelets (Derived from Complete Blood Count).
- Creatinine, Alk Phos, AST, ALT, BUN, Bilirubin (Derived from Complete Metabolic Panel).
- Pill count to assess adherence.
- Samples of stool (collected at home or at clinic) to be sent to the central laboratory are collected and processed:
 - Stool for quantitative Norovirus RT-PCR and sequencing.
 - Stool for other pathogen testing; stool will be stored for later testing and this assay will not be performed for formed stool after Day 1.
- Nitazoxanide PK drawn 1-4 hours after the subject takes his/her dose, for subjects consenting to this optional assessment. The time of the blood draw and the time of the previous dose will be recorded.
- Vital signs (temperature, BP, respiration, weight and pulse) will be obtained.
- Weekly Recall Packet will be administered (Table 5).
- Collect concurrent medications.
- Inquiry about hospitalization since last assessment.
- Assess for adverse events.

c. Study Day 14 ± 3 days: Virtual Visit

- Team to call subject

- Review of completed diary pages.
- Subject to collect stool sample and store in freezer until day 28 study visit
- Weekly Recall Packet will be administered (Table 5).
- Collect concurrent medications.
- Inquiry about hospitalization since last assessment.
- Assess for adverse events.

d. Study Day 21 ± 3 days- Virtual Visit except for patients who agree to optional PK study

- Team to call subject not enrolled in the PK Sub Study (those patients will have in person visit)
- Review of completed diary pages.
- Subject to collect stool sample and store in freezer until day 28 study visit.
- For patients in the PK Sub Study:
 - Samples of stool to be sent to the central laboratory are collected and processed:

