27. For subjects consenting to PK draws, concentrations of nitazoxanide metabolites (tizoxanide and tizoxanide glucuronide) 1 to 4 hours after the first dose on Day 7 and 10 minutes before the second dose on Day 21.

Natural History of Disease:

28. Time to allograft rejection as per each center team.
29. Time to graft loss as reported to UNOS.
30. Time to death.
31. Time to withdrawal from the study because of intolerance or drug related adverse events.
32. Correlation of secretor status as defined by phenotype and genotype, separately and clinical resolution of Norovirus as defined by the primary endpoint.

Clinical Improvement:

For exploratory outcomes 1 through 5, Kaplan-Meier curves will be produced along with results from a Log-Rank test to compare the time from randomization to clinical improvement in Norovirus disease between the nitazoxanide treated group and the placebo group. The Cox proportional hazards model will be used to estimate the corresponding hazard ratio and 95% confidence interval. If baseline demographic variables are shown to be unbalanced among the treatment groups, those variables will be adjusted in the Cox model.

For exploratory outcomes 6-8, if the number of days of diarrhea follows an approximately normal distribution, then the average number of days will be estimated and compared between the two groups. If the number of days of diarrhea does not follow a normal distribution, a Poisson distribution or non-parametric analysis such as the Wilcoxon test will be considered.

For exploratory outcomes 9, if number of days of hospitalization follows an approximately normal distribution, then the average number of days will be estimated and compared between groups using a two-sample t-test. If the number of days of hospitalization does not follow a normal distribution, a Poisson distribution or a non-parametric analysis such as the Wilcoxon test will be considered.

For exploratory outcomes 10-13, subjects will complete Detailed PRO and Symptom Severity questionnaires at each visit to track changes over time in each of the psychosocial and QOL constructs. An ANCOVA model will be fit using the two groups as the between-subjects factor, time as the within-subjects factor and baseline scores as a covariate. In addition, groups will be compared on unadjusted change over time using a mixed-design analysis of variance (ANOVA) model with all times, including baseline, as a repeated measures factor. Of interest is whether

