Serum Immunoglobulin Testing (Serum total Ig and Norovirus-specific levels): Day 1 will assess baseline values, Day 28 will assess end of treatment levels. The proportion of subjects with ≥ 4 -fold rise in Norovirus-specific Ig titers from Day 1 will be assessed at Day 28 comparing

the nitazoxanide treatment group to the placebo group. In addition, the ratios of Norovirus-specific IgG to total IgG will also be compared between the nitazoxanide and placebo groups.

For exploratory outcome 22, an ANCOVA model will first be used to compare the treatment and placebo groups with respect to difference in changes of Norovirus-specific serum and stool IgA, IgM and IgG between Day 1 and Day 28 and between Day 1 and Day 60 (for stool only). A mixed effects model will then be used to compare the treatment and placebo groups with respect to difference in the changes of Norovirus-specific serum and stool IgA, IgM and IgG, which will use the longitudinal data observed at all three time points.

For exploratory outcomes 23-26, a Fisher's Z-transformation will be applied to the Pearson correlations between change in total lymphocyte count and T cell subsets at Day 1 and 180 and clinical resolution of symptoms in both the treatment and placebo groups, which will then be compared using a Z-test.

Pharmacokinetics and Dose Response:

For exploratory outcome 27, plasma concentrations of nitazoxanide metabolites in subjects consenting for PK blood draws at two time points will be described and summarized. Descriptive statistics (e.g. n, mean, standard deviation, % CV, median, and range) will be calculated for each sampling time.

Cox proportional hazard regression models will be used to examine the dose response relationship of Day 7 and Day 21 nitazoxanide metabolite concentrations on time from randomization until initial clinical resolution of Norovirus symptoms for at least 48 hours through Day 180. Additional analyses of PK endpoints may be described in the SAP.

Natural History of Disease:

Exploratory outcomes 28-31 are all time-to-event outcomes. They will be analyzed similarly as exploratory outcome 1.

Exploratory outcome 32 will be assessed similarly to exploratory outcome 14.

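### The exposure-response Cox model counts time from randomization but uses Day 7 and Day 21 drug levels, so earlier resolutions are attributed to a level measured after them

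*Protocol*

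**What the plan says.** The outcome and the covariate are set out in Protocol section 11.4.5 (Pharmacokinetics and Dose Response): "Cox proportional hazard regression models will be used to examine the dose response relationship of Day 7 and Day 21 nitazoxanide metabolite concentrations". The model relates "metabolite concentrations on time from randomization until initial clinical resolution of Norovirus symptoms for at least 48 hours through Day 180". The levels are those taken "1 to 4 hours after the first dose on Day 7 and 10 minutes before the second dose on Day 21". The visit windows in the Protocol Summary are "study visits on study Day 1, 7 ± 3 days, 14 ± 3 days, 21 ± 3 days", so the draws fall on Days 4 to 10 and Days 18 to 24. Section 7.1 describes the first sample: "Nitazoxanide PK drawn 1-4 hours after the subject takes his/her dose, for subjects consenting to this optional assessment". The second is a pre-dose trough (Appendix A). For both, section 7.1 asks for the time of the draw and of the previous dose; it does not mention food.

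Section 7 fixes the course: "All subjects must have therapy discontinued after taking 56 doses". A subject who has already recovered is therefore still dosed and still sampled.

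On food, section 2.1 reports: "Administration of the tablet with food increased the AUC_t of tizoxanide and tizoxanide glucuronide in plasma almost two-fold", with Cmax up by almost 50%. The regimen is given as with food in several places, but section 7 also says: "Subjects will take study product preferably with food for 56 consecutive doses", and section 6.2 allows water for a patient who is NPO.

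Section 11.4.5 offers time-varying coding for co-pathogens but not for drug levels. The SAP (sections 1 and 6.2) moves all PK analysis to an addendum that is not among the documents.

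**The concern.** A covariate measured on Day 7 or Day 21 is used as if it were known at randomization. A subject who resolves on Day 5 contributes an event on Day 5, explained by a level drawn later. No landmark, delayed entry or time-varying coding prevents this.

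The timing error alone does not create a false association. It does so if recovery changes the level. Food is a candidate route: a recovered patient may eat more and so absorb more. Resolution would then raise the later level, and the model would read this as higher exposure causing faster resolution. The trial has one dose level, so this is the only analysis stated for the dose-response part of the PK objective. What is at stake is a biased exploratory estimate that could inform later dose thinking. The primary result is not affected.

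**Working it through.** **1. The plan's own figure.** The PK model has no stated sample size, power or error rate. The medians used below are those behind the primary sample size (Protocol 11.2: 135 and 67.5 days), and under exponential times they reproduce it.
- Resolved by Day 180: 1 − 2^(−180/135) = 0.603 on placebo and 1 − 2^(−180/67.5) = 0.843 on nitazoxanide, mean 0.723.
- Events: 128 × 0.723 = 92.5.
- Power: Φ(√(92.5/4) × ln 2 − 1.96) = Φ(1.37) = 91.5%, against 90% stated and 91.3% in the table cell with no additional treatment.
- Attrition: 128 / 0.80 = 160.

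**2. Share resolved before the draw**, 1 − 2^(−t/median):

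| Median | Day 4 | Day 7 | Day 10 | Day 18 | Day 21 | Day 24 |
|---|---|---|---|---|---|---|
| 67.5 d (planning, nitazoxanide) | 4.0% | 6.9% | 9.8% | 16.9% | 19.4% | 21.8% |
| 12.5 d (pediatric series, section 2.1) | 19.9% | 32.2% | 42.6% | 63.1% | 68.8% | 73.6% |

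At the planning median, these early events are 0.069/0.843 = 8.2% (Day 7) and 0.194/0.843 = 23.0% (Day 21) of all resolutions by Day 180.

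**3. Null simulation of the model as written.** Resolution times are exponential, censored at Day 180 and unrelated to exposure. The level is log-normal and is multiplied by a food factor if the subject is fed. Resolved subjects are always fed; unresolved subjects are unfed with probability q.
- CV 19% is adult tizoxanide Cmax, 2.0/10.6 (Table 3). CV 67% is ages 12 to 17, 6.1/9.1, used only as a wide bound because no pediatric subjects were enrolled.
- Food factor 1.5 at Day 7 follows the Cmax effect. Food factor 2 at Day 21 is an assumption, because the documents give no food effect for a trough.
- q has no source, so the full range is shown.

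Hazard ratio per doubling, median 67.5 days, n = 400:

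| q | Day 7, CV 19% | Day 7, CV 67% | Day 21, CV 19% | Day 21, CV 67% |
|---|---|---|---|---|
| 0 | 0.99 | 1.00 | 0.98 | 1.00 |
| 0.25 | 1.10 | 1.01 | 1.23 | 1.06 |
| 0.5 | 1.18 | 1.02 | 1.39 | 1.10 |
| 1 | 1.84 | 1.06 | 6.58 | 1.30 |

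The last row assumes that no unresolved subject ever doses with food, which is an extreme bound.

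**4. Other assumptions, same median.** With 90% of resolved and 50% of unresolved subjects fed, CV 19% and food factor 2, the Day 21 ratio is 1.31. It falls to 1.12 if 70% of unresolved subjects eat. At CV 40% it is 1.08 to 1.16 for food factors 1.2 to 2.0, and the Day 7 ratio is 1.03 to 1.06. If symptoms resolve faster (median 12.5 days, q = 0.5, n = 400), the ratios are 1.09 to 1.65 at Day 7 and 1.21 to 2.06 at Day 21.

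**5. Planned PK size.** Section 8.2.2 asks for a 20% sample: 0.20 × 160 = 32, about 16 on drug. At n = 16, median 67.5 days and q = 0.5, the two-sided 5% test rejects 5% to 6% of the time for Day 7 and 6% to 11% for Day 21.

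**6. Landmark version.** Starting the clock at the draw among subjects still unresolved gives ratios of 0.97 to 1.02 in every n = 400 scenario. Rejection is 2% to 8% over 300 runs each (Monte Carlo error about 1.3 points). At n = 16 and median 67.5 days, rejection is 4% to 6%. This follows by construction, since the simulation contains only the mechanism that a landmark removes.

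**The case against.** The strongest reply is that the governing text may already be different. The SAP places PK in an addendum, and that addendum could have replaced this model. This stands: a reader might infer that the flawed model is the final one, but the documents show only that nothing supplied withdraws it.

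The second reply is about size. This is one exploratory outcome of 32, in a convenience sample, and SAP section 6.6 reports that enrolment stopped at 31. The number with PK data is unknown: about 3 on drug if 20% of those enrolled (0.20 × 31 / 2), and at most about half of 31 if everyone was sampled. At such sizes a false-positive test is not the main worry. This also stands.

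The third reply is that the bias route is inferred. The documents establish the food effect on AUC and Cmax. They do not show that recovered subjects are more often fed at dosing, and they give no food effect on a trough. A reader might infer from the word preferably in section 7 that fasted dosing was common, but the same section and section 6.2 also state the regimen as with food. With q = 0 the model is mistimed but unbiased under the null.

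A reader might also infer that the 1 to 4 hour window misses the peak, because adult glucuronide Tmax is 4.5 h (range 4 to 6). For tizoxanide, Table 3 gives 3.0 h (range 2 to 4), inside the window.

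None of this answers the timing error. Subjects who resolved before the draw still enter with a later level.

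**Conclusion.** The timing error is in the Protocol text, and the supplied SAP does not correct it. It affects about 7% of nitazoxanide subjects for the Day 7 model and 19% for the Day 21 model at the planning median, and more if symptoms resolve faster.

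The resulting bias is conditional. If feeding at the dose depends on recovery, illustrative null hazard ratios per doubling at the planning median are about 1.1 to 1.4 for Day 21 and 1.0 to 1.2 for Day 7. They depend on the assumed CV, the food effect on a trough and the diet split. Without that dependence there is no bias.

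The stronger claim, that the trial will report a false exposure-response, is not supported: the link to recovery is undocumented, the test is little disturbed at the planned PK size, and the addendum is unseen. I rate this a minor correction to an exploratory analysis, with moderate confidence.

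**What to change.** In the PK addendum, if it has not already replaced this model:
- Fit separate Day 7 and Day 21 landmark models in nitazoxanide-arm subjects with PK data. The Protocol does not say whether placebo subjects enter. The near-peak and trough values should not be treated as the same exposure measure.
- Start time at the actual draw and include only subjects unresolved at that draw.
- Account for the recorded time since the last dose.
- Use the daily diary question on usual diet (SAP section 3.3) only as a day-level proxy for fed state. It does not say whether the sampled dose, or the dose before the trough, was taken with food.
- Prespecify the analyte after reconciling section 2.1, which lists tizoxanide glucuronide among the active metabolites and later calls it non-active.
- Report descriptively if too few subjects remain. At a 12.5-day median, 16 subjects on drug would leave about 5 at Day 21 (16 × 0.312).

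The cost is addendum wording. Subjects resolved before the draw leave this model: about 7% at Day 7 and 19% at Day 21 on the planning median. The landmark removes the reversed timing only. The comparison stays observational, because among unresolved subjects those eating better may also have a better prognosis.

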12 SOURCE DOCUMENTS AND ACCESS TO SOURCE DATA/DOCUMENTS

Each participating site will maintain appropriate medical and research records in compliance with ICH E6, Section 4.9 and regulatory and institutional requirements for the protection of confidentiality of subjects. Each site will permit authorized representatives of the DMID, its designees, and appropriate regulatory agencies to examine (and when required by applicable law, to copy) clinical records for the purposes of quality assurance reviews, audits, and evaluation of the study safety and progress. These representatives will be permitted access to all source data and source documents, which include, but are not limited to, hospital records, clinical and office charts, laboratory notes, memoranda, subjects' memory aid or evaluation checklists, pharmacy dispensing records, recorded data from automated instruments, copies or transcriptions certified after verification as being accurate and complete, microfiches, photographic negatives, microfilm or magnetic media, x-rays, and subject files and records kept at the pharmacy, at the laboratories, and medico-technical departments involved in the clinical trial.

13 QUALITY CONTROL AND QUALITY ASSURANCE

Following a written DMID-accepted protocol-specific quality management plan, each investigational site is responsible for conducting routine quality control (QC) and quality assurance (QA) activities to internally monitor study progress and protocol compliance. Each site Principal Investigator will provide direct access to all protocol-related source data/source documents, and reports for the purpose of monitoring and auditing by the sponsor, and inspection by local and regulatory authorities. Each site Principal Investigator will ensure all study personnel are appropriately trained and current documentations are maintained on site.

DMID-designated clinical monitors will verify the clinical trial data are generated, documented (recorded), and reported in compliance with the protocol, Good Clinical Practice standards, and the applicable regulatory requirements. Clinical monitoring reports will be submitted to DMID.

The Statistical and Data Coordinating Center (SDCC) will implement quality control procedures beginning with the data entry system; database quality control checks will be implemented. Any missing data or data anomalies will be communicated to the site(s) for clarification and resolution.

